(0.8 mT) magnet to protect against stray external magnetic fields (pictured below). The filling pressure of the gas allows 1 L of useable gas when released. The container is then shipped to the imaging center where it is transferred to the tedlar bags and administered to the subject. This system has been previously tested successfully in Europe and Australia. (21, 22)

Hypothesis to be Tested

The purpose of this study is to further develop the technique of rapid hyperpolarized helium-3 MRI for use in infants, and perform a pilot study in infants who are healthy and infants with CF, BPD, and asthma.

Study Design: Biomedical

1. Will controls be used? No.

2. What is the study design?

Pilot.

3. Does the study involve a placebo?

No.

Human Participants

Ages: 1 month -65 years old

Sex: Both

Race: All

Subjects- see below

- 1. Provide target # of subjects (at all sites) needed to complete protocol.** 110.
- 2. Describe expected rate of screen failure/ dropouts/withdrawals from all sites.** 10%.

- 3. How many subjects will be enrolled at all sites?** 121.
4. How many subjects will sign a consent form under this UVa protocol? 121.
- 5. Provide an estimated time line for the study.** We expect to complete this study in 5 years.

Inclusion/Exclusion Criteria

1. List the criteria for inclusion

We confirm that this protocol includes two arms: 1) one that enrolls adults and children age >1 month to fine tune the details of the MRI sequence acquisitions and 2) a pilot study that enrolls infants and young children age >1 month with either healthy or diseased lungs. Some of the subjects in arm 2 may be on a ventilator and ready to wean.

MRI sequence development (n=60):

Healthy subjects and patients with CF, BPD, asthma, COPD, a history of smoking or other lung diseases will be used in the development of the rapid imaging techniques. These subjects will be age 1 months to 65 years old. Healthy subjects can have no history of chronic respiratory disease. The subjects with CF, asthma, or BPD must have a physician diagnosis of their respective disease.

Pilot Study (n=50):

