Twenty healthy infants, 10 infants with CF, and 20 infants with BPD age 1-24 months will be imaged in the proof-of-concept study. Healthy infant must have had an uncomplicated term birth and have no history of chronic respiratory symptoms. Infants with BPD must have a physician diagnosis of BPD. The patients with CF must have a physician diagnosis of CF and be at their baseline clinical status on the day of imaging. In order to enroll infants with normal lungs who are being ventilated, we will include infants with a perinatal hypoxic ischemic event (HIE) as healthy subjects.

Some subjects may be invited to return for an additional MR imaging visit and the subsequent follow up (as described below) after approximately 5 months from their first visit. Before this is done, the participant will sign the consent form again.

If a child is on a ventilator, they must either meet the criteria for being ready to be weaned from the ventilator or clinically stable on a home ventilator. An MRI compatible ventilator will be used while the patient is in the scanner.

2. List the criteria for exclusion

- Any condition for which a MRI procedure is contraindicated.
- Presence of any non-MRI compatible metallic material in the body, such as pacemakers, metallic clips, etc.
- Likelihood of claustrophobia.
- Chest circumference greater than that of the helium MR coil.
- Pregnancy, by report of subject. Clinically in the Department of radiology at UVA, self-report is used when screening patients for MR scans as well as CT scans and fluoroscopy studies. If the subject

reports there is any chance of their being pregnant, a urine pregnancy test will be performed prior to any imaging.

3. List any restrictions on use of other drugs or treatments.

Inhaled medications such as short acting beta-2 agonists should not be administered within 4 hours prior to the hyperpolarized helium-3-MRI.

Statistical Considerations

1. Is stratification/randomization involved? No.

2. What are the statistical considerations for the protocol?

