The goals of this project are to further develop the technique of hyperpolarized helium-3 MRI for use in infants and to perform a small pilot study in 30 infants to demonstrate the technique could be expanded to a larger clinical trial. No formal statistical analyses are planned. For the images obtained as part of the proof-of-concept study, we will measure conventional metrics of image quality such as signal-to-noise ratio (SNR) to quantify the image quality obtained with our technique. However, no comparison with our historical data in cooperative, older subjects is planned. In addition, we will calculate as a measure of disease severity, the percent of the lung volume that is poorly ventilated.

3. Provide a justification for the sample size used in this protocol.

The sample size for the MRI sequence development portion of this study is derived from our long experience in developing new techniques for hyperpolarized gas MRI. Best guess estimates are initially used for the sequence parameters but the sequences must be tested and refined in human subjects because the complex interactions of the lung microstructure, the hyperpolarized gas signal characteristics, and sequence parameters are difficult to predict, so much trial and error is used in the development. The sample size for the proof-of-concept trial is the smallest number to demonstrate that the technique is both feasible and robust in both healthy infants and infants with lung disease.

4. What is your plan for primary variable analysis?

No formal statistical analyses will be required, and none are planned.

5. What is your plan for secondary variable analysis?

We will compare the measures of image quality and disease severity between the 10 healthy infants, the 10 infants with CF, and the 10 infants with BPD. However, we do not expect there to be significant differences between these two groups with this low number of subjects.

6. Have you been working with a statistician in designing this protocol? No.

7. Will data from multiple sites be combined during analysis? No.

Biomedical Research

1. What will be done in this protocol?

All study procedures, including MR imaging, will take place at the Snyder Building at Fontaine Research Park or the main radiology department in the hospital.

- A medical history will be taken defining any present and past history of respiratory illnesses, medications, and hospitalizations and the ability to have MR imaging.

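### The pilot is sized at 50 infants in the inclusion criteria but at 30 in the opening summary and the Statistical Considerations; only 50 reproduces the stated totals of 110 and 121

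*Combined protocol and SAP*

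**What the plan says.** Two sets of statements describe the same proof-of-concept study.

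**Fifty infants.** Inclusion/Exclusion Criteria item 1 heads one part "MRI sequence development (n=60") and the other "Pilot Study (n=50"), and splits the second as "Twenty healthy infants, 10 infants with CF, and 20 infants with BPD". Under Human Participants, item 1 reads "Provide target # of subjects (at all sites) needed to complete protocol. 110", item 2 reads "Describe expected rate of screen failure/ dropouts/withdrawals from all sites. 10" (per cent), and item 4 reads "How many subjects will sign a consent form under this UVa protocol? 121". Item 3 there gives the same 121 for enrolment at all sites.

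**Thirty infants.** The opening summary, before the Background section, gives 60 subjects for sequence development and a further 30 for the proof of concept, 10 per group. Statistical Considerations item 2 describes a pilot in 30 infants without a split. Item 5 compares image quality and disease severity "between the 10 healthy infants, the 10 infants with CF, and the 10 infants with BPD".

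Three other statements bear on the point:
- Statistical Considerations item 3 justifies the proof-of-concept size as a minimum for showing feasibility and robustness, but names no number.
- Items 2 and 4 say that no formal analysis is planned.
- The inclusion criteria add that "Some subjects may be invited to return for an additional MR imaging visit", about 5 months after the first.

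**The concern.** A study can have only one pilot size, and here the enrolment part and the statistical part disagree. Nothing in the text says that the 30 are a subset of the 50. Both counts are of infants to be imaged, so they are not an enrolled number and an evaluable number.

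Two things depend on the answer.

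- **The comparison.** Item 5 is the only between-group comparison in the plan. If 50 infants are imaged and item 5 is followed as written, 10 of 20 healthy infants and 10 of 20 infants with BPD have to be chosen, and no rule says how.
- **The justification.** Item 3 is the only argument for the size of the pilot. A minimum cannot be both 30 and 50. If it was written for 30, the other 20 infants have no stated justification. They would inhale an investigational gas in a study whose Risk/Benefit Analysis expects no direct benefit to participants.

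Item 5 also names three groups and then refers to two. This may mean healthy against diseased, as item 3 puts it, but the text does not say so.

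**Working it through.** **Inputs**

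| Quantity | Value | Where |
|---|---|---|
| Sequence development | 60 | Opening summary; Inclusion/Exclusion Criteria item 1 |
| Pilot, first count | 20 + 10 + 20 = 50 | Inclusion/Exclusion Criteria item 1 |
| Pilot, second count | 10 + 10 + 10 = 30 | Opening summary; Statistical Considerations item 5 (item 2 gives the total only) |
| Target to complete | 110 | Human Participants item 1 |
| Expected losses | 10% | Human Participants item 2 |
| Enrolled and consented | 121 | Human Participants items 3 and 4 |

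**Step 1. Reproduce the stated totals.** Target = sequence development + pilot. Enrolment = target × (1 + 0.10).

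- Pilot of 50: 60 + 50 = 110, and 110 × 1.10 = 121. Both match exactly.
- Pilot of 30: 60 + 30 = 90, and 90 × 1.10 = 99. Neither matches.

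**Step 2. Check the other way of allowing for losses.** Enrolment = target / (1 − 0.10).

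- Pilot of 50: 110 / 0.90 = 122.2, rounded up to 123. This is close to 121 but not equal to it.
- Pilot of 30: 90 / 0.90 = 100. This is far from 121.

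The exact fit indicates that the protocol multiplied by 1.10. Under either convention a pilot of 30 does not lead to 110 or 121.

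**Step 3. Can losses turn 30 into 50?** 30 × 1.10 = 33, and 30 / 0.90 = 33.3, rounded up to 34. Neither is near 50. An allowance for losses would also have raised the CF group, which is 10 in both counts.

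**Step 4. Size of the gap**

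| | Pilot of 50 | Pilot of 30 | Difference |
|---|---|---|---|
| Healthy | 20 | 10 | 10 |
| CF | 10 | 10 | 0 |
| BPD | 20 | 10 | 10 |
| Pilot total | 50 | 30 | 20 (20/50 = 40%) |
| Target | 110 | 90 | 20 |
| Enrolment (× 1.10) | 121 | 99 | 22 |

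**Step 5. What the group sizes mean for item 5.** The plan gives no power or significance level, so this is an illustration only. It assumes a two-sided 5% level, 80% power, a normal approximation and no adjustment for multiple comparisons. The detectable standardised difference is (1.96 + 0.84) × √(1/n₁ + 1/n₂).

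- 10 against 10: 1.25 standard deviations.
- 20 against 10: 1.09.
- 20 against 20: 0.89.

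Under these assumptions only large differences would be detectable at either size. Item 5's warning about small numbers is therefore weaker at 20/10/20, but not overturned.

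**The case against.** The strongest reply is that the extra 20 infants may be deliberate. They are exactly 10 healthy and 10 with BPD. The inclusion criteria admit ventilated infants and count those with a perinatal hypoxic ischemic event as healthy, so that ventilated infants with normal lungs can enrol. The opening summary defers ventilator-dependent infants under one year until the IRB has reviewed other infant data. The 10/10/10 in item 5 could then be a comparison restricted to non-ventilated infants. No passage says this, however, and the opening summary, which gives 30, itself covers ventilated infants. The reading does not remove the contradiction. It does show that changing item 5 to 20/10/20 would put ventilated infants and infants with a hypoxic ischemic event into the comparison unless the text says otherwise.

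Other points are fair but secondary:

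- No sum in the protocol is miscalculated. The fault is disagreement between sections, and 90 and 99 are derived here, not stated in the document.
- Item 3 states no number and so contradicts none. It only fails to show which size it supports.
- The reference to two groups, and the question of which scan to use, would need attention even if the counts agreed.
- With no formal analysis, no decision rule and consistent figures under Human Participants, the practical effect is small. This stands.

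**Conclusion.** The plan is wrong as written: it gives 50 and 30 for the same pilot. The difference is 20 infants, 40% of the larger figure, and it falls entirely in the healthy and BPD groups. The totals of 110 and 121 agree with a pilot of 50 and not with one of 30.

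That 50 is the intended size is an inference. It rests on sequence development being 60, which both parts of the protocol state, and on the target being the sum of the two parts. The arithmetic does not prove what the investigators meant.

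The discrepancy should be corrected because it affects the only sample-size justification and the only between-group comparison. The consequence is limited. The comparison is descriptive, the enrolment figures agree with one another, and item 2 applies the image-quality measures to the proof-of-concept images without naming a subset.

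**What to change.** State one pilot size throughout.

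**If 50 is intended**, as the totals indicate:
- Change the opening summary and Statistical Considerations items 2 and 5 to 50 infants (20 healthy, 10 CF, 20 BPD).
- Put the number into item 3, and confirm that the minimum-size argument there and the small-numbers remark in item 5 still apply at 20/10/20.
- In item 5, say which infants and which scan enter the comparison. One option is all imaged pilot infants at their first visit. Say also whether ventilated infants, and those with a hypoxic ischemic event who are counted as healthy, are included. These choices are for the investigators.
- Say whether item 5 compares three groups or two.

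This costs wording and a short re-check of the justification. It adds no infants and no procedures.

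**If 30 is intended**, restate the pilot in the inclusion criteria as 30 (10/10/10), the target as 90 and enrolment as 99. The number in item 3, the scan and the groups compared still need to be stated. The target falls by 20 and planned enrolment by 22.

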- A urine pregnancy test will be done for women of childbearing potential, who report the possibility that they might be pregnant.
- If needed, a practice bag filled with room air will be given to the subject as a teaching tool to teach the subjects the breathing technique used during the administration of hyperpolarized helium gas.
- Before and after MR imaging, a physical exam, spirometry (if subject able to perform test), and a baseline %PO₂ will be performed.
- During the MR imaging procedure, the subject's heart rate and blood oxygen saturation will be monitored using an MR compatible pulse oximeter when possible.
- Once positioned in the MR scanner, the free breathing MR imaging will be performed.
- Then, the hyperpolarized helium 3 imaging will be performed.
 - Subjects who are infants will be bundled or held to restrain motion while in the MRI scanner
 - Infants will be placed in the MR coil such that their head is supported in a neutral position. Imaging occurs very quickly so the total time the subject is expected to be in the scanner is less than 15 minutes.
 - For infants with BPD, a physician from the research team will be present at all imaging sessions to monitor the subject. Imaging will be terminated if the physician feels the baby is being unusually stressed in any way.
 - Imaging will be terminated and oxygen given if the subject's pO₂ on pulse oximetry drops by 10% or more or if there is a sustained low heart rate over one minute of less than 100 bpm heart rate. We have experience with MR imaging of young infants for clinical brain MRI and most infants tolerate imaging of the brain MRI well. We expect infants to tolerate the lung imaging well particularly since the duration of imaging will be less than brain MRI.
 - If the subject is not on a ventilator, the subject will inhale the hyperpolarized gas which may be mixed with medical grade nitrogen through a small plastic tube connected to a plastic bag containing the hyperpolarized gas mixture or through a face mask or other gas delivery device. If the subject is on a ventilator the hyperpolarized gas mixture will be introduced into the ventilator circuit just before the endotracheal or tracheostomy tube.
 - Rapid MR imaging will be performed during inhalation/exhalation and/or breath-hold. Depending upon the availability of gas and the quality of images obtained, the helium-3 inhalation and MR imaging may be repeated.

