- The PI will inform the subjects verbally of all incidental findings that are of clinical significance or are of questionable significance.
- A follow-up letter describing the finding should be provided to the subject with instructions to either show the letter to their PC or if the subject has no PCP, the subject should be instructed to make an appointment at UVa or at the Free Clinic.

This examination(s) utilizes non-standard/investigational, technique, equipment, etc. It is impossible to determine the significance of such results, therefore abnormalities will not be shared with the subject because the meaning of the exam is not yet proven and is of unknown clinical benefit. (Helium MRI)

6. Do any of the procedures listed above, under question # 2, utilize any imaging procedures for RESEARCH PURPOSES? Yes.

IF YES, list procedures:

MRI with helium.

This imaging research examination utilizes non-standard/investigational imaging modality, techniques, equipment, scanning sequences, etc. It is impossible to determine the significance of such images, therefore abnormalities will not be shared with the subject because the meaning of the exam is not yet proven and is of unknown clinical benefit.

7. Will you be using viable embryos? No.

8. Will you be using embryonic stem cells? No.

9 Are any aspects of the study kept secret from the participants? No.

10. Is any deception used in the study? No.

11. If this protocol involves study treatment, explain how a subject will be transitioned from study treatment when they have completed their participation in the study.

NA, study does not involve a treatment.

12. Will your study involve measures (C-SSRS/BID/SCID etc.) used to assess for depression and/or suicidality for research purposes? No.

13. Where will the study procedures be done?

Check One:

UVA medical center facilities (In patient or outpatient)
 UVa , but not medical center facilities: LIST specific location Snyder Building

14. If the study involves medical risk and study procedures will be done outside of the UVa Medical Center what is your plan to protect the subjects in case of a medical emergency?

Study coordinator onsite during procedures
 Individual trained in CPR on site during procedures
 AED and Individual trained to use it onsite
 Call 911

Specimens

Specimen Information

1. Describe the type of specimen to be used: urine

2. Will the specimen be obtained BEFORE a subject has signed a consent form? No

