
 This coil, which is necessary to obtain the MR images of the lungs with the hyperpolarized gas, transmits and receives radio waves at much lower power than used with most standard MRI techniques. The coil is considered by the manufacturer a non-significant risk device, but it has not been approved by the FDA. 	 Occurs frequently,  Occurs infrequently  Occurs rarely  Frequency unknown
--	--

Risk related to Spirometry	

 Since spirometry requires blowing hard several times, the subject may cough or feel short of breath during or after the test. 	 Occurs frequently,  Occurs infrequently  Occurs rarely  Frequency unknown

Risk to a fetus	

 For females: At present, the safety of hyperpolarized gas to a fetus has not been established. If you are pregnant or nursing you may not participate in this study. 	 Occurs frequently,  Occurs infrequently  Occurs rarely  Frequency unknown

 For males: You should not father a baby while you are in this study or for one month after your participation in the study ends 	 Occurs frequently,  Occurs infrequently  Occurs rarely  Frequency unknown

Risk of Transport	

 Risk of dislodgement of the endotracheal tube Unplanned extubation 	 Occurs frequently,  Occurs infrequently  Occurs rarely  Frequency unknown

2.2 List by bullet format a summary of safety tests/procedures/observations to be performed that will minimize risks to participants:

- Medical History questionnaire
- Pre and post inhalation measurement of spirometry
- Pre and post inhalation measurement of oxygen saturation monitoring (pulsoximetry)

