- For MRI scanning: Participants need to complete the standard MR questionnaire that is also used at the clinical sites to screen the individuals ineligible for MRI scanning: This screens for metallic foreign bodies, inner ear implants, pacemakers, claustrophobia, etc.

- For MR scanning with inhaled hyperpolarized helium-3. Individuals whose body habitus does not allow the person to fit in the special vest coils for imaging at the MR frequency of hyperpolarized helium-3 are excluded. In case of doubt the vest coil will be fitted around the participant outside the scanner to determine eligibility.
- Follow-up for adverse events is performed within 1 to 5 days post imaging by telephone or email contact.
- All NICU infants, whether or not they are on a ventilator, will be transported to MRI per standard clinical care procedures and NICU personnel will remain with the infant during imaging per standard care.

2.3 Under what criteria would an INDIVIDUAL SUBJECT'S study treatment or study participation be stopped or modified

At subject, PI or sponsor's request

2.4 Under what criteria would THE ENTIRE STUDY need to be stopped.

Per IRB, PI, DSMB, or sponsor discretion

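### The numeric rule for ending a scan relies, during the scan, on an oximeter required only where possible, and the available text does not hold gas when there is no trace

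*Combined protocol and SAP*

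**What the plan says.** Under Biomedical Research, question 1, monitoring in the scanner is described as follows: "During the MR imaging procedure, the subject's heart rate and blood oxygen saturation will be monitored using an MR compatible pulse oximeter when possible". The stop rule is in the same list. Its saturation limb reads "Imaging will be terminated and oxygen given if the subject's pO₂ on pulse oximetry drops by 10% or more", and its heart-rate limb applies to a "sustained low heart rate over one minute of less than 100 bpm heart rate". The protocol writes pO₂ on oximetry; I read that as oxygen saturation.

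The same list lets inhalation and imaging be repeated according to how much gas is available and how good the images are. The pharmacy appendix (items 3 to 5) allows up to 10 doses per session, each inhalation and breath-hold lasting about 20 seconds or less.

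Other safeguards are stated:

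- Data and Safety Monitoring Plan, 2.2: "Pre and post inhalation measurement of oxygen saturation monitoring (pulsoximetry" is listed without any qualifier.
- Biomedical Research, question 1: "Before and after MR imaging, a physical exam, spirometry (if subject able to perform test), and a baseline %PO₂ will be performed".
- Same list: "For infants with BPD, a physician from the research team will be present at all imaging sessions to monitor the subject", with a stop if that physician finds the baby unusually stressed.
- Data and Safety Monitoring Plan, 2.2: for NICU infants, "NICU personnel will remain with the infant during imaging per standard care".
- Biomedical Research, question 14, lists a study coordinator, "Individual trained in CPR on site during procedures", a defibrillator with a trained user, and a 911 call. The tick marks are not legible in the text.
- Data and Safety Monitoring Plan, 2.3: the subject, the PI or the sponsor can ask for participation to stop.

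**The concern.** The stop rule is mandatory, but the measurement that drives it during the scan is not. In an unsedated infant who is bundled or held, losing the oximeter signal is a foreseeable event, and the plan gives no instruction for it. Lack of a trace is not an exclusion criterion, an individual stopping criterion or a condition on the next dose.

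The hazard is one the protocol itself names. Section 2.1 lists a saturation fall of more than 10% among the expected, rare effects of inhaling the gas. The gas is helium-3, possibly mixed with nitrogen, and no oxygen in the mixture is stated. Infants cannot report symptoms. At stake is a fall or a slow heart rate going unseen while further doses are given.

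**Working it through.** There is no figure in the plan to reproduce. The check sets the stop rule against each stated safeguard and asks what each could detect if the in-scan trace were absent.

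**1. Is gas conditional on a trace?** No. The conditions for repeating inhalation are gas supply and image quality. The exclusion criteria, section 2.3 and the pharmacy appendix add no monitoring condition. Parts of the background and of the pharmacy appendix, and the case report forms, were not available to me, so this is a statement about the available text.

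**2. Saturation limb without a trace.** The rule speaks of a fall on pulse oximetry and does not confine itself to the in-scan device. The readings in section 2.2 can therefore trigger it. How far they help depends on what that item means:

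- *A pair around each inhalation:* a fall that persists after dose 1 is seen before dose 2, and the rule acts.
- *The same single pair as the readings before and after imaging:* a persisting fall is seen only at the end of the session.

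On either meaning, a fall that has recovered by the time of the reading is missed. The pharmacy appendix (item 13b) describes past falls as mild and transient, and a dose lasts about 20 seconds or less. Oxygen may also be given immediately after inhalation (Biomedical Research, question 1), which can correct the reading before it is taken.

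**3. Heart-rate limb without a trace.** Section 2.2 names saturation only. The rule needs a low rate sustained over 60 seconds, which is at least 60 / 20 = 3 times the length of a dose. A spot reading cannot show that, so no stated measurement supports this limb once the trace is lost.

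**4. Who is watching?** A physician is stated for infants with BPD, and NICU staff for NICU infants. For the remaining pilot infants no attending clinician is stated. As upper bounds:

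- Inclusion criteria: 20 healthy + 10 CF = 30 of 50 (30 / 50 = 60%).
- Statistical Considerations: 10 healthy + 10 CF = 20 of 30 (20 / 30 = 67%).

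The true number is lower to the extent that these infants are NICU patients. Ventilated infants with a perinatal hypoxic ischemic event, for example, are counted as healthy. The emergency provisions in question 14 respond to a recognized emergency; they do not measure saturation or heart rate.

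**5. How likely is the event?** Section 2.1 rates a fall above 10% as occurring rarely. The pediatric review reports 6 events at least possibly related to helium in 121 children (6 / 121 = 5.0%), all mild and not serious. Item 13b reports events in 78 of 818 studies (78 / 818 = 9.5%), mostly mild, with children no more likely than adults to have one. It also says the lowest saturation was within 10% of baseline in most cases, which is not all. None of these figures is broken down for infants.

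**The case against.** The strongest reply is that the plan is not blind when the trace is lost. A reader might infer that the stop rule then cannot act at all; the documents do not support that, because the oximetry around inhalation in section 2.2 is unconditional and can trigger the saturation limb for a persisting fall. A reader might also multiply infants by 10 doses and call the result unmonitored exposure. That is not supported either. Ten is a ceiling, infants are expected to be in the scanner for less than 15 minutes, and no trace-loss rate is given.

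It is also fair to say that silence about a clinician is not absence of one. A physical exam is required before and after imaging, which implies a qualified examiner at the visit, and the PI can stop at any time. Past events were mostly mild. A compulsory trace could end some sessions in infants who will not keep a probe on, against the aim of imaging without sedation.

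All of this lowers the expected harm and limits the size of the point. It does not supply a reading for the heart-rate limb, does not catch a transient or oxygen-corrected fall, and does not tell staff what to do when the signal disappears.

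**Conclusion.** The concern holds in a limited form. During the scan the numeric stop rule relies on an oximeter that need not be working, and the available text lets gas continue without it. The uncovered part is the heart-rate limb, together with saturation falls that are brief or masked by oxygen. Healthy and CF infants outside the NICU are the most exposed.

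Expected risk is low on the protocol's own data, with the reservation that those data are not infant-specific. The conclusion assumes that the unavailable pages and forms contain no rule to hold gas. It does not depend on any assumed rate of signal loss.

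A reader might take this for a flaw in the analysis. It is not: Statistical Considerations plans no formal analysis, and saturation is not among the measures named there. It is a cheap patient-safety improvement that should be made.

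**What to change.** In Biomedical Research, question 1, for infants, replace the qualifier on in-scan monitoring with a requirement along these lines: a readable saturation and heart-rate trace must be present before each helium dose, and if the trace is lost no further dose is given until it returns. The existing wording can remain for older children and adults. The option to give oxygen is protective and should stay.

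Optional additions are to state that the 10% fall is measured from the pre-imaging baseline, to record for each dose whether a trace was present, and to list untraced doses in the infant data that the IRB must approve before ventilator-dependent infants are enrolled. The main fix does not depend on them.

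The cost is one or two sentences, using equipment already in the plan. The downside is that some sessions in restless, unsedated infants may be delayed, shortened or not completed.
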